6. GENERAL CONSIDERATIONS

6.1. REFERENCE START DATE AND STUDY DAY

Study Day will be calculated from the reference start date, and will be used to show start/ stop day of assessments and events. It will appear in every listing where an assessment date or event date appears.

Reference start date is defined as the day of the first dose of trial medication, (Day 1 is the day of the first dose of trial medication), or for subjects randomized but not treated it is the day of randomization.

- If the date of the event is on or after the reference date then:

Study Day = (date of event – reference date) + 1.

- If the date of the event is prior to the reference date then:

Study Day = (date of event – reference date).

In the situation where the event date is partial or missing, Study Day, and any corresponding durations will appear partial or missing in the listings.

6.2. BASELINE

Unless otherwise specified, baseline is defined as the last non-missing measurement taken prior to reference start date (including unscheduled assessments) except for the primary efficacy endpoint (refer to section 15.1.2.2). In the case where the last non-missing measurement and the first dose of trial medication date coincide, that measurement will be considered as baseline.

6.3. RETESTS, UNSCHEDULED VISITS AND EARLY TERMINATION DATA

In general, for by-visit summaries, data recorded at the nominal visit will be presented. In the case of a retest, an unscheduled assessment will be created. For laboratory assessments as described in APPENDIX 5, the latest available measurement within 2 days after the planned assessment will be used for by-visit summaries. Unless assigned to a planned visit number, unscheduled measurements will not be included in by-visit summaries except for DILIs (refer to section 16.3).

Subjects who are terminated from the study early will have their End of Treatment (EoT) visit on a date which may or may not coincide with the window designated for one of the 8 regular planned visits.

Remapping of EOT visit assessment data to a regular scheduled visit will be performed only if the EOT visit

Document: \\eedc-nas01a:\Boehringer_Ingelheim\BI_695501\XXA39605\Biostatistics\Documentation\SAP\15
-v2.0\BI 1297.12 SAP v2.0 31JAN2018.docx

Author: Version Number: 2.0
Version Date: 31JAN2018

Template No: CS_TP_BS016 Revision 4
Effective Date: 01Apr2016

Reference: CS_WI_BS005

assessment was performed during the window for a regular scheduled visit and if the assessment value is non-missing for each regular planned visit between the last regular planned visit for which it was non-missing and the date of the EOT visit. Otherwise, the data will be classified as Early Termination and identified as such in the relevant listings.

If a subject's EOT visit for an assessment was performed in the window designated for a regular planned visit X and the last time point prior to visit X at which the assessment was to have been performed, according to the study flow chart, is the last regular planned visit for which it was non-missing then the assessment's value will be mapped to visit X, if it is an assessment that is scheduled to be performed at visit X.

If a subject's EOT visit for an assessment was performed at some time point after the window designated for a regular planned visit X and before the window designated for a regular planned visit X + 1 and the last time point prior to visit X + 1 at which the assessment was to have been performed, according to the study flow chart is the last regular planned visit for which it was non-missing then the assessment's value will be mapped to visit X + 1, if it is an assessment that is scheduled to be performed at visit X + 1.

Listings will include scheduled, unscheduled, and retest data as collected in the eCRF database.

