6. INVESTIGATIONAL PLAN

6.1 VISIT SCHEDULE

A schedule of assessments is provided in the [Flow Chart](#).

Each visit date (with its window) is to be counted from Day 1 (randomization). If any visit has to be rescheduled, the 2-week regimen for trial medication administration should resume from the time the last dose was administered. Additional visits for the purpose of re-testing of laboratory parameters or AE monitoring may be included as deemed necessary by the investigator.

- A visit window of -1 / + 2 days is permitted for Visit 2 (Day 1)
- A visit window of ± 2 days is permitted from Visit 3 up to Visit 7
- A visit window of ± 3 days is permitted for Visit 8 to Visit 10

All assessments should be performed prior to administration trial medication, unless otherwise specified. Laboratory samples must be drawn prior to trial medication injection.

The questionnaire will be completed at the site by the patient (DLQI) before any investigations or discussions about their disease with the clinic staff and may only be recorded by a trial nurse/investigator on behalf of the patient if the patient has difficulty writing during the visit or is unable to read. This must be documented clearly in the patient notes.

Also the scales are to be completed by study site personnel (PASI sPGA,

All questionnaires and scales are detailed in Appendix 10.

The total estimated volume of blood that will be drawn from each patient during the course of the trial is shown in [Table 6.1: 1](#).

Table 6.1: 1 Estimated blood sample volumes per patient

Parameter	Sample volume (mL)	Number of samples	Total volume (mL)
Laboratory tests (including serum chemistry, serum pregnancy test)	3	6	18
Hematology	3	6	18
Infection screen	4	1	4
TB test	3	2	6
Approximate total			82

Abbreviations: ADA=anti-drug antibodies; nAb=neutralizing ADA; TB=tuberculosis.

Additional samples may be required if medically indicated, e.g., at unscheduled visits to follow safety findings.

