7.3.4 Safety analyses

Adverse events will be coded using the Medical Dictionary for Drug Regulatory Activities (MedDRA). The analysis of AEs will be based on the concept of treatment-emergent AEs. That means that all AEs with an onset between start of treatment and end of the REP, a period of 10 weeks after the last dose of trial medication, will be assigned to the treatment

period for evaluation. AEs that start before first drug intake and deteriorate under treatment will also be considered as ‘treatment-emergent’. Other AEs will be assigned to the appropriate trial phases, i.e., screening or post-treatment.

All treated patients will be included in the safety analysis. In general, safety analyses will be descriptive in nature and will be based on BI standards. No hypothesis testing is planned.

Statistical analysis and reporting of adverse events will concentrate on treatment-emergent adverse events. To this end, all adverse events occurring between start of treatment and end of the residual effect period will be considered ‘treatment-emergent’. The residual effect period is defined as 10 weeks after last dose of trial medication. Adverse events that start before first drug intake and deteriorate under treatment will also be considered as ‘treatment-emergent’.

Frequency, severity, and causal relationship of adverse events will be tabulated by system organ class and preferred term after coding according to the current version of the Medical Dictionary for Drug Regulatory Activities (MedDRA).

Laboratory data will be analysed both quantitatively as well as qualitatively. The latter will be done via comparison of laboratory data to their reference ranges. Values outside the reference range as well as values defined as clinically relevant will be highlighted in the listings. Treatment groups will be compared descriptively with regard to distribution parameters as well as with regard to frequency and percentage of patients with abnormal values or clinically relevant abnormal values.

Vital signs, physical examinations, or other safety-relevant data observed at screening, baseline, during the course of the trial and at the end-of-trial evaluation will be assessed with regard to possible changes compared to findings before start of treatment.

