10.1.2 Procedures

Repeat the following laboratory tests: ALT, AST, and bilirubin (total and direct) - within 48 to 72 hours. If it is confirmed that ALT and/or AST values ≥ 3 times ULN occur in conjunction with an elevation of total bilirubin of ≥ 2 times ULN, the laboratory parameters listed below (clinical chemistry, serology, hormones, haematology) must be determined and made available to the investigator and to BI as soon as possible.

In addition,

- obtain a detailed history of current symptoms and concurrent diagnoses and medical history according to the 'DILI checklist' provided in the ISF
- obtain history of concomitant drug use (including non-prescription medications, herbal and dietary supplement preparations), alcohol use, recreational drug use, and special diets according to the 'DILI checklist' provided in the ISF;
- obtain a history of exposure to environmental chemical agents (consider home and work place exposure) according to the 'DILI checklist' provided in the ISF;

and report these via the CRF.

Clinical chemistry

Alkaline phosphatase, albumin, PT or INR, CK, CK-MB, coeruloplasmin, α -1 antitrypsin, transferin, amylase, lipase, fasting glucose, cholesterol, triglycerides

Serology

Hepatitis A (Anti-IgM, Anti-IgG), Hepatitis B (HbsAg, Anti-HBs, DNA), Hepatitis C (Anti-HCV, RNA if Anti-HCV positive), Hepatitis D (Anti-IgM, Anti-IgG), Hepatitis E (Anti-HEV, Anti-HEV IgM, RNA if Anti-HEV IgM positive), Anti-Smooth Muscle antibody (titer), Anti-nuclear antibody (titer), Anti-LKM (liver-kidney microsomes) antibody, Anti-mitochondrial antibody

Hormones, tumor marker

TSH

Hematology

Thrombocytes, eosinophils

- Provide abdominal ultrasound to rule out biliary tract, pancreatic or intrahepatic pathology, e.g. bile duct stones or neoplasm.
- Initiate close observation of subjects by repeat testing of ALT, AST, and total bilirubin (total and direct) at least weekly until the laboratory ALT and/or AST abnormalities stabilize or return to normal, then monitor further as specified in the CTP. Depending on further laboratory changes, additional parameters identified, e.g., by reflex testing will be followed up based on medical judgement and GCP.

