16.3. LABORATORY EVALUATIONS

Results from the central laboratory will be included in the reporting of this trial for Serum Chemistry, Hematology and Urinalysis. A list of laboratory assessments to be included in the outputs is included in APPENDIX 5.

Presentations will use SI and US Units.

Quantitative laboratory measurements reported as “< X”, i.e., below the lower limit of quantification (BLQ), or “> X”, i.e., above the upper limit of quantification (ULQ), will be converted to X for the purpose of quantitative summaries, but will be presented as recorded, i.e., as “< X” or “> X” in the listings.

Qualitative laboratory urinalysis results measured by central laboratory will be classified to the categories “Positive” and “Negative” based on the central laboratory normal reference.

The handling of retests, unscheduled, and end of trial measurements is described in Section 6.3. However, laboratory values taken after the first dose of trial medication up to the end of a period (i.e. up to 10 weeks after the last dose of the trial medication) will be assigned to the treatment phase for evaluation. Moreover, tables about DILI will include unscheduled visits.

All available data will be listed.

The following summaries will be provided for laboratory data:

- Actual and change from baseline by visit (for quantitative measurements)
- Shifts from baseline category (Low/ Normal/ High) by visit (except for urinalysis)

Document: \\eedc-nas01a:\Boehringer_Ingelheim\BI_695501\XXA39605\Biostatistics\Documentation\SAP\15-v2.0\BI 1297.12 SAP v2.0 31JAN2018.docx

Author: Version Number: 2.0
Version Date: 31JAN2018

Template No: CS_TP_BS016 Revision 4
Effective Date: 01Apr2016

Reference: CS_WI_BS005

- Shift from baseline category (Negative/ Positive) by visit (for urinalysis)
- Listing of subjects meeting abnormal criteria
- Proportion of possible Hy's law subjects
- Proportion of possible Drug Induced Liver Injuries (DILIs)
- The time course of ALT, AST and total bilirubin (TBL) for all possible Hy's law subjects, all parameters shown on a logarithm to base 10 scale of the multiple of the upper limit of normal (ULN) (Y axis) versus days since treatment start (X axis).
- Scatter plots for Evaluation of Potentially Drug-Induced Liver Injury:
 - log ALT on the X axis and log TBL on the Y axis, both shown on a logarithm to base 10 scale of the multiple of the ULN

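### By-visit laboratory tables can understate transient abnormalities, and the SAP only partly delivers the protocol's comparison of patients with abnormal values

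*SAP*

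**What the plan says.** **Which value enters a by-visit table (SAP 6.3).** The general rule is that by-visit summaries use the data recorded at the nominal visit. For retests, "In the case of a retest, an unscheduled assessment will be created". The laboratory parameters of SAP Appendix 5 then get their own rule: "the latest available measurement within 2 days after the planned assessment will be used for by-visit summaries". For everything else, "Unless assigned to a planned visit number, unscheduled measurements will not be included in by-visit summaries except for DILIs". Listings keep scheduled, unscheduled and repeat values.

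**When repeats happen.** Protocol 6.1: "Additional visits for the purpose of re-testing of laboratory parameters or AE monitoring may be included as deemed necessary by the investigator". The same section allows extra samples at unscheduled visits to follow safety findings. Protocol 6.2.3 has abnormal values that the investigator judges clinically relevant monitored until they are medically acceptable. For the liver alert, Protocol 10.1.2 says: "Repeat the following laboratory tests: ALT, AST, and bilirubin (total and direct) - within 48 to 72 hours". No routine duplicate sampling is planned.

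**What is to be reported.** Protocol 7.3.4 commits to comparing the groups descriptively on "frequency and percentage of patients with abnormal values or clinically relevant abnormal values". SAP 16.3 lists actual values and changes by visit, "Shifts from baseline category (Low/ Normal/ High) by visit (except for urinalysis", a negative/positive shift for urinalysis, "Listing of subjects meeting abnormal criteria", and proportions of possible Hy's law and DILI cases. SAP 16.3.2 has abnormal criteria in its title but defines only Low, Normal and High.

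**The concern.** Two things combine.

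First, the rule that picks the tabulated value depends on whether a repeat was taken, and repeats are more likely after an abnormal result. Suppose a neutrophil count is low at Week 8 and back in range two days later. The Week 8 shift table then shows that patient as Normal. Part of such normalisation is regression to the mean, and part is a real but short-lived abnormality. A safety table should show the latter.

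Second, no planned summary would pick these values up again for haematology, renal function or most chemistry. The tables are per visit, and the output for patients meeting abnormal criteria is a listing. A listing gives no frequency by arm. At the Week 16 primary analysis, SAP 4.1 excludes patient-level data, so listings would not support the tables then.

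At stake is the descriptive laboratory comparison, which belongs to the secondary safety objective. The PASI 75 equivalence conclusion is not affected.

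**Working it through.** The documents give no figure for this point, so there is nothing to reproduce. The check is a comparison of texts, followed by an illustration on assumed inputs.

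**Step 1. Commitment against planned output**

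| Protocol 7.3.4 | SAP 16.3 / 16.3.2 |
|---|---|
| Patients with abnormal values, frequency and %, by group | Counted visit by visit in the shift tables; no any-time table |
| Patients with clinically relevant abnormal values, frequency and %, by group | No table, and no criteria |
| Out-of-range and clinically relevant values highlighted in listings | Listing of subjects meeting abnormal criteria |

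SAP 16.3 also assigns values up to 10 weeks after the last dose to the treatment phase for evaluation, but no listed summary is tied to that sentence.

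**Step 2. Effect of the 2-day rule**

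Let *p* be the share of scheduled values above the limit, *r* the share of those repeated within 2 days, and *s* the share of the repeated highs that come back inside the limit. If only highs are repeated:

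tabulated rate = *p* × (1 − *r* × *s*)

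None of these inputs is in the documents. I assume *p* = 5%, and first and repeat values that are bivariate normal with correlation ρ. Then *s* is the probability that the repeat lies below the 95th percentile, given that the first value lies above it.

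| ρ | *s* | *r* = 0 | *r* = 10% | *r* = 30% | *r* = 50% |
|---|---|---|---|---|---|
| 0.95 | 0.26 | 5.0% | 4.9% | 4.6% | 4.4% |
| 0.90 | 0.36 | 5.0% | 4.8% | 4.5% | 4.1% |
| 0.80 | 0.50 | 5.0% | 4.7% | 4.2% | 3.7% |
| 0.70 | 0.61 | 5.0% | 4.7% | 4.1% | 3.5% |

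Example: ρ = 0.70 and *r* = 50% give 5% × (1 − 0.5 × 0.61) = 3.5%. With about 150 patients per arm (300 randomized 1:1), that is 7.5 expected patients falling to about 5.2.

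**Step 3. Repeats of values that were normal**

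If a panel is redrawn, values that were first normal are replaced too. Let *r*N be the share of normal values repeated within 2 days. If first and repeat values are exchangeable, the chance of normal-then-high equals that of high-then-normal, which is *p* × *s*. Hence:

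tabulated rate = *p* × [1 − *s* × (*r* − *r*N)]

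The understatement comes only from highs being repeated more often than normals. Step 2 is the case *r*N = 0.

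**Step 4. What an any-time table would add**

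Safety laboratory tests fall at four post-baseline points: Visits 5, 7 and 9 (Weeks 8, 16 and 24) and the safety follow-up. At an assumed 5% per visit, the share of patients ever abnormal is 5% if the same patients are abnormal each time, 1 − 0.95⁴ = 18.5% if visits are independent, and 4 × 5% = 20% if different patients are abnormal each time. Per-visit tables cannot tell these apart.

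**The case against.** The case on the other side is substantial.

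- **The reason for a repeat is not stated in the SAP, and its frequency is not stated anywhere.** A 2-day window also suits redraws of unusable samples. Samples go to a central laboratory, so a repeat prompted by a result may seldom fall within 2 days. This stands against any claim about size. It weakens the direction less, because Protocol 6.1, 6.2.3 and 10.1.2 tie repeats mostly to abnormal or safety findings.
- **Liver findings are mostly protected.** DILI tables include unscheduled visits, Hy's law counts any time point, and liver repeats at 48 to 72 hours fall at or beyond the edge of the window. This stands, but only for elevations that reach those thresholds.
- **Clinically significant abnormalities are reported as adverse events** (Protocol 5.3.3) and so reach the AE tables. This stands, subject to the investigator's judgement.
- **Protocol 7.3.4 does not say any-time or worst value**, and the by-visit shift tables do count patients by arm. This stands: the commitment is partly met. The clinically relevant count is still absent.
- **The table templates that accompany the SAP are not available here** and might add outputs. SAP 16.3 lists none.

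A reader might infer more than the documents support:

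- *That every replacement moves toward Normal.* The rule takes the latest value, so a worse repeat is used as well, and redrawn panels can turn normals into abnormals (Step 3).
- *That abnormal data are lost.* All values remain in the listings.
- *That the rule makes the arms look alike, which would matter in an equivalence trial.* Equivalence rests on PASI 75 alone. On the model above, arms at 5% and 10% with half of the highs repeated are tabulated at 3.5-4.4% and 7.3-8.9%. The difference shrinks from 5.0 to about 3.9-4.5 points, but the ratio rises slightly from 2.0.

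**Conclusion.** The point holds in a limited form. By-visit laboratory tables can understate transient abnormalities outside the DILI and Hy's law outputs, because a repeat within 2 days replaces the scheduled value and most other unscheduled values are left out. The direction rests on abnormal results being repeated more often than normal ones, which the protocol's text supports.

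The size is unknown. On the assumed inputs, a 5% rate is tabulated as 4.1-4.9% when 10-30% of highs are repeated in the window and as 3.5-4.4% when half are. It stays at 5% when none are. This is a range of illustrations, not an estimate.

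The gap between documents needs no assumption about repeats. Protocol 7.3.4 commits to comparing patients with abnormal or clinically relevant abnormal values. The SAP text gives per-visit counts and a listing, without an any-time table or a clinically relevant count, and without criteria for the latter. This is a shortfall in descriptive safety reporting that is cheap to repair. It does not threaten the trial's main conclusion.

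**What to change.** 1. **SAP 6.3:** use the scheduled-visit sample for by-visit laboratory summaries. Take a repeat only when the scheduled sample is missing or was reported as technically invalid.
2. **SAP 16.3:** add one table by arm showing the shift from baseline to the worst on-treatment value. The window is first dose to last dose + 70 days, which matches the treatment phase that SAP 16.3 already describes. Include scheduled, repeat and unscheduled values.
3. **SAP 16.3 and 16.3.2:** in the same table, give the number and percentage of patients with clinically relevant abnormal values, and have the sponsor state the criteria in 16.3.2. The worst-value shift alone would not meet the protocol's wording.

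The cost is one changed sentence, a set of stated criteria and one extra table, all from data already collected. Some transient abnormalities will become visible, so the laboratory tables may look slightly less favourable.

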6.4. WINDOWING CONVENTIONS

Unless otherwise specified, visit data as recorded in the database will be used for the analysis. No visit windowing recalculation will be performed for this trial.

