14.1. DERIVATIONS

Compliance with trial medication will be based on the eCRF page “Trial Medication Injection”. An administered injection is considered when the question “Was full dose given” is answered “Yes”.

Compliance will be based on the comparison of actual administered injections and the planned usage. Compliance will include visits until treatment discontinuation.

- “Per visit” compliance will be calculated as follows and will correspond to the observed compliance between visit N and N-1:

Compliance (%) = (Number of administered injections at visit X) * 100 / Planned number of injections at visit X

Planned usage is detailed below.

- “Overall” compliance will be calculated as follows:

Compliance (%) = (Number of administered injections) * 100 / Planned number of injections

Where

Planned usage

Visit N	1	2	3	4	5	6	7	8	9
---------	---	---	---	---	---	---	---	---	---

Document: \\eedc-nas01a:\Boehringer_Ingelheim\BI_695501\XXA39605\Biostatistics\Documentation\SAP\15-v2.0\BI 1297.12 SAP v2.0 31JAN2018.docx

Author: Version Number: 2.0
Version Date: 31JAN2018

Template No: CS_TP_BS016 Revision 4
Effective Date: 01Apr2016

Reference: CS_WI_BS005

Number of injections between visit N and N-1	-	2	1	1	2	2	2	2	2
Planned cumulative number of injections	0	2	3	4	6	8	10	12	14

- “Week 16” compliance will be calculated considering the injections until Week 16 (visit 7) (included).

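### SAP 6.3 gives two incompatible rules for an End of Treatment assessment that falls between visit windows; this affects the Week 16 percentage PASI improvement and the by-visit tables, not the equivalence conclusion

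*SAP*

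**What the plan says.** SAP 6.3 covers patients who leave early and whose EoT visit may not coincide with a planned visit.

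- **First rule.** The condition is exclusive: "Remapping of EOT visit assessment data to a regular scheduled visit will be performed only if the EOT visit" (the sentence continues over a page break) "assessment was performed during the window for a regular scheduled visit and if the assessment value is non-missing for each regular planned visit" since the last non-missing one. Where it is not met: "Otherwise, the data will be classified as Early Termination and identified as such in the relevant listings".
- **Last paragraph of the same section.** It takes an EoT assessment made "after the window designated for a regular planned visit X and before the window designated for a regular planned visit X + 1" and maps its value to visit X + 1. This applies if the value at the preceding scheduled time point was not missing and the assessment is due at visit X + 1.

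SAP 6.4 uses visit data as recorded unless otherwise specified, and adds: "No visit windowing recalculation will be performed for this trial".

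Two further places set the boundary for Week 16. SAP 14.1 identifies Week 16 as Visit 7: "compliance will be calculated considering the injections until Week 16 (visit 7) (included"). Protocol 6.1 says: "A visit window of ± 2 days is permitted from Visit 3 up to Visit 7". The protocol's Flow Chart instead allows ±3 days at Week 16 (Day 113) and ±2 days at Week 12 (Day 85).

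**The concern.** The two rules cover the same assessments and give opposite answers. An EoT PASI on Day 90 is an Early Termination value under the first rule. Under the last paragraph it is a Week 16 value, about three weeks before Week 16. Two programmers could each follow the SAP and produce different datasets.

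The output would not show which rule was used: SAP Appendix 1 has the listings display the eCRF visit rather than the remapped one.

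At stake is which patients, and which values, enter the analyses that take the Week 16 record at face value. The forward mapping also works as an imputation that is not declared as one.

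**Working it through.** No figure stated in the plan is at issue, so there is none to reproduce. The check compares the texts, counts days and sizes the effect.

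**1. Can the two rules be read together?** No. The first rule is closed: it allows remapping only inside a window and sends every other case to Early Termination. The last paragraph begins from an assessment outside every window. It is not introduced as an exception. SAP 6.4 yields to anything specified elsewhere, so it supports neither rule over the other.

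**2. Disputed days for Week 16** (PASI, sPGA and DLQI, all scheduled at Weeks 12 and 16)

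- The Week 12 window ends on Day 85 + 2 = 87.
- The Week 16 window opens on Day 113 − 3 = 110 (Flow Chart) or Day 113 − 2 = 111 (Protocol 6.1, since Week 16 is Visit 7).
- The disputed days are therefore 88-109 (22 days) or 88-110 (23 days).

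The same conflict arises in the other gaps between visits, for example between Weeks 20 and 24.

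**3. Which endpoints are exposed?**

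| Analysis | Treatment of a patient who stopped before Week 16 | Exposed? |
|---|---|---|
| PASI 75 at Week 16 (SAP 15.1.2) | Non-responder, whether or not a Week 16 value can be computed | Not directly |
| sPGA and DLQI at Week 16 (SAP 15.2.2) | Non-responder imputation combined with LOCF | No |
| Percentage PASI improvement at Week 16, M2 (SAP 15.2.3.2) | No rule named in SAP 15.2.2 | Yes, if analysed without imputation |
| By-visit efficacy and safety summaries | Governed by SAP 6.3 itself | Yes |

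One indirect route to the primary analysis remains. Multiple imputation is run on continuous PASI up to Week 16 before the non-responder step. A mapped value could therefore help fit the model that imputes other patients. This effect should be small.

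**4. Size for M2.** The documents give no stopping rate, timing or EoT values. Assumptions: 150 per arm; 5% or 10% stopping before Week 16; stop day uniform on Days 9-109 (101 days); half or all stoppers with an EoT PASI; M2 without imputation; no missed Week 12 values.

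Expected number of patients affected = 300 × stopping rate × share with an EoT PASI × 22/101:

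- 5%, all: 300 × 0.05 × 0.218 = 3.3
- 10%, all: 300 × 0.10 × 0.218 = 6.5
- 5%, half: 1.6
- 10%, half: 3.3

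The between-arm difference in mean percentage improvement was then simulated with and without the Day 88-109 values (5,000 trials per row, equal stopping in both arms). Completers were drawn from Normal(82, 22) and stoppers from Normal(mean shown, 30), both clipped to −50 to 100. The standard error of the difference was about 2.2 points throughout.

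| Stopping per arm | With EoT PASI | Stoppers' mean improvement | SD of shift (points) | P(shift > 0.5 SE) |
|---|---|---|---|---|
| 5% | half | 50% | 0.4 | 1% |
| 10% | half | 50% | 0.6 | 5% |
| 5% | half | 30% | 0.5 | 5% |
| 10% | half | 30% | 0.75 | 14% |
| 5% | all | 50% | 0.5 | 5% |
| 10% | all | 0% | 1.6 | 47% |

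With equal stopping the mean shift is about zero. With 10% against 5% stopping and all stoppers assessed, there is also a mean shift of 0.4 to 1.0 points as the stoppers' mean goes from 50% to 0%. With half assessed, it is 0.2 to 0.5 points.

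**The case against.** **No decision rests on this.** The primary endpoint is protected, and the protocol synopsis says secondary efficacy is interpreted descriptively. The secondary safety endpoint, drug-related adverse events, does not depend on visit mapping. All of this stands and limits the point to a descriptive endpoint and the tables.

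**The larger effects need unlikely inputs.** Protocol 3.3.4.1 ends all investigations when consent is withdrawn, and Protocol 6.2.3 gives an EoT visit only to those who do not withdraw consent. So not every stopper has an EoT PASI. The last row of the table also assumes no average improvement after about three months of treatment. This stands too; the rows with half assessed are more realistic.

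**The M2 effect belongs partly to another gap.** It assumes that M2 has no imputation. Protocol 7.3.2.1 puts all secondary analyses on the FAS with non-responder imputation, but that gives no value for a continuous percentage. If scores were carried forward, an EoT value might enter under either rule. This is fair, and it is why the fix must also settle M2.

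**Three stronger readings that a reader might infer are not supported.**

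- That the rule could be picked after results are known. Under SAP 4.1 a blinded team writes the Week 16 programs before an independent statistician applies the randomization schedule. SAP 4.2 repeats those analyses at the end, and nothing describes reopening the mapping.
- That most early stops change a Week 16 value. With the Flow Chart windows, 84 of the 101 days from Day 9 to Day 109 (83%) lie outside every window. That counts days, not patients, and only 22 of the 101 (22%) bear on Week 16.
- That the equivalence conclusion is threatened. Step 3 of the working shows why it is not.

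**Conclusion.** The contradiction is real, and SAP 6.3 cannot be programmed as written without choosing a paragraph. Its reach is limited. It changes who contributes, and with what value, to M2 (if analysed without imputation) and to the by-visit efficacy and safety summaries. It leaves the PASI 75, sPGA and DLQI status of these patients unchanged, apart from a possible small indirect effect on the primary analysis through the imputation model.

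Under the assumptions in the working, about 2 to 7 patients are affected and the M2 difference typically moves by a fraction of its standard error of about 2.2 points. Those figures rest on assumed stopping rates, timing and values, none of which the documents supply. The existence of the conflict rests on the text alone. It is worth correcting because the correction is cheap.

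**What to change.** - **SAP 6.3:** keep one rule. The better choice is to map only EoT assessments made inside a visit window. Delete the between-window paragraph and show Early Termination as its own row in the by-visit tables, so that these values are not confined to listings. The documents do not show which rule was intended; the reason for this preference is that an earlier value should not become a Week 16 value through visit labelling.
- **SAP 6.4:** align it with the rule kept.
- **Week 16 window:** the Flow Chart and Protocol 6.1 must be reconciled and a single window used; otherwise the in-window rule has no fixed boundary.
- **SAP 15.2.2:** state how M2 handles patients who stop early. A value from before the Week 16 window should enter M2 only through a declared imputation rule. Whether to impute, and how, is a separate choice on which statisticians may differ.

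The cost is a change of SAP wording, one programming rule and the reconciliation of the window, with no new data. The downside is that a few early stoppers no longer supply a moved-forward value at the next visit. Without an imputation rule, M2 would move closer to a completers' analysis, which is a further reason to settle that rule at the same time.
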